## 5. OVERALL CONSIDERATIONS

All summary tables and data listings produced by INC will use the statistical package SAS (v9.2 or a more recent version).

In general, categorical data will be presented using counts and percentages, whilst continuous data will be presented using the descriptive statistics, mean, standard deviation (SD), median, minimum, maximum and number of patients with an observation (n). Minimum and maximum values will be quoted to the number of decimal places as recorded on the CRF; means, medians and SDs will be quoted to one further decimal place. Percentages will be rounded to one decimal place. Percentages smaller than 0.1 will be presented as <0.1. Percentages whose numerator is zero will be reported as zero.

All data recorded on the Case Report Form (CRF) and any derived data will be listed for all patients.

The Safety population will be used to present Adverse Event and death data. The PP population will be used to present all data .

Unless otherwise stated missing data will not be imputed. Patients who withdraw prematurely will have their data summarized at the last attended visit. Repeat assessments will not be summarized unless otherwise indicated but will be fully listed. Similarly, data collected at unscheduled visits will be listed only. Repeat and unscheduled visits will be identified on the data listings.

Where of interest, presentation of data will be pooled to reflect the target cell type, CD4 cells in OZ1-HV1-101 and CD34 cells in OZ1-HV1-102 and OZ1-HV1-202 in addition to presenting separately and overall.

<Protocol: Janssen OZ1-HV1-101/102/202>

<INC code: 1003733>

<SAP Version: 3.0>

---

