### 6.4. OTHER INITIAL STUDY INFORMATION

Treatment details (date of infusion, dose, treatment and transduced efficiency) from the original studies are recorded as part of the initial study information. Patients in 101 originally received a single dose of transduced CD4+ lymphocytes and patients in 102 and 202 originally received a single dose of CD34+ cells.

Time since infusion (years) will be derived using the following formula:

$$(\text{Date of Last Visit in Long Term Follow-up} - \text{Date of Infusion}) / 365.25$$

Time since infusion, dose, transduction efficiency and calculated dose will be summarized using descriptive statistics, mean, median, standard deviation, minimum, maximum and n by cell type (CD4 or CD34). Calculated dose will be derived as follows:

$$\text{Dose (CD4+ or CD34+)} / 100 \times \text{transduction efficiency}$$

<Protocol: Janssen OZ1-HV1-101/102/202>

<INC code: 1003733>

<SAP Version: 3.0>

---

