### 7.2. METHODS OF ANALYSIS

#### 7.2.1. Analysis of Marking in Peripheral Blood Mononuclear Cells

For OZ1 & LNL6 DNA-PCR (marking) the number and percentage of patients in each of the categories Not Detected, Detected (1/3 Detected, 2/3 Detected, 3/3 Detected) and Detected (Quantifiable). The number and percentage of patients in each category will be presented at each timepoint for 102/202 combined and overall for the PP population.

Patients who have quantifiable OZ1 & LNL6 DNA-PCR detected will have the value listed and the relationship between the % marking and calculated dose, age at infusion, gender and race explored as described below.

Correlation between OZ1 & LNL6 DNA-PCR (%) and calculated dose will be assessed using PROC CORR in SAS. The number of patients with quantifiable detected and calculated dose data, Spearman's rank correlation co-efficient and its associated p-value will be presented. Similar presentations will be made for OZ1 & LNL6 DNA-PCR (%) versus age and OZ1 & LNL6 DNA-PCR (%) and time since infusion (as defined in Section 6.3).

Association between the number of patients with and without OZ1 & LNL6 DNA-PCR quantifiable detection and gender will be assessed by the Chi-Squared test using PROC FREQ in SAS. The number of patients with data for both parameters, the Chi-Square statistic and its associated p-value will be presented. A p-value of less than 0.05 will indicate an association between the parameters. Similar presentations will be made for OZ1 & LNL6 DNA-PCR versus race and gender. If it is not appropriate to perform the Chi-Square test due to small cell sizes, Fishers Exact test will be performed.

<Protocol: Janssen OZ1-HV1-101/102/202>

<INC code: 1003733>

<SAP Version: 3.0>

---

The above analyses will be performed for 102/202 combined and overall at each post infusion timepoint for the PP population providing there are patients with quantifiable data to render the analyses meaningful. A review of the marker data will take place at the Data Review Meeting. All decisions taken regarding the above analyses will be fully documented in the meeting minutes.

The percentage of patients detected with either a quantifiable or non quantifiable OZ1 & LNL6 DNA-PCR result will be plotted over time for 101, 102 and 202 separately, 102/202 combined and overall for the PP population.

<Protocol: Janssen OZ1-HV1-101/102/202>

<INC code: 1003733>

<SAP Version: 3.0>

---

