3 years post infusion	Analysed Sample	n	
	Not Detected	n (%)	
	Etc...		

Note: Data summarized in this table are presented in data listing x.x

\* = OZ1 & LNL6 DNA Detected but below the lower quantitative limit of the assay: 1/3 = 1 of the 3 triplicates of the sample were detected; 2/3 = 2 of the 3 triplicates of the sample were detected; 3/3 = 3 of the 3 triplicates of the sample were detected.

DDMMYYYY HH:MM

*Prgm note: % based on N*

*Programming note: Please repeat this table for 14.2.1.1a (Study 202 only)*

<Protocol: Janssen OZ1-HV1-101/102/202>

<INC code: 1003733>

<SAP Version: 3.0>

Janssen - OZ1-HVI-101/102/202

TABLE 14.2.1.2

Page x of y

OZ1 and LNL6 DNA PCR  
Relationship Between Marking Parameters (PBMC) and Calculated Dose, Age, Time on Study, Gender and Race  
Summary Statistics: PP Population

Visit	PBMC versus	Statistic	OZ1-HV1-102 / OZ1-HV1-202 (N = XX)	Overall (N = XX)
2 years post infusion	Calculated Dose	N (1) Rho (2) p-value		
	Age (3)	N (1) Rho (2) p-value		
	Time on Study	N (1) Rho (2) p-value		
	Gender	N (1) Chi-Square (4) p-value		
	Race (5)	N (1) Chi-Square (4) p-value		
2.5 years post infusion Etc..	Calculated Dose	N (1) Rho (2) Etc..		

Note: Data summarized in this table are presented in data listing x.x  
 (1) N = number of patients with quantifiable OZ1 & LNL6 DNA detected  
 (2) Rho = Spearman's Rank Correlation co-efficient  
 (3) = Age at infusion

<Protocol: Janssen OZ1-HV1-101/102/202>

<INC code: 1003733>

<SAP Version: 3.0>

---

(4) = Chi-Square statistic

(5) = Race categories (Aboriginal, African American, American Indian, Asian, Caucasian, Hispanic, Maori/Polynesian, Other  
DDMMYYYY HH:MM

*Prgm note: Fishers Exact test may be presented if Chi-Square test is not appropriate*

*Programming note: Please repeat this table for 14.2.1.2a (Study 202 only)*

<Protocol: Janssen OZ1-HV1-101/102/202>

<INC code: 1003733>

<SAP Version: 3.0>

Janssen - OZ1-HVI-101/102/202

TABLE 14.3.1

Page 1 of x

Overall Summary of Adverse Events  
Summary Statistics: Safety Population

	OZ1-HV1-101 (N=xx)	OZ1-HV1-102 (N=xx)	OZ1-HV1-202 (N=xx)	Overall (N=xx)
Number (%) of patients with at least one SAE				
Number (%) of patients with at least one related SAE				
Number (%) of patients with at least one severe related SAE				
Number (%) of patients with least one NSRAE				
Number (%) of patients with SAE/NSRAE leading to death				
Number of SAEs				
Number of related SAEs				
Number of severe related SAEs				
Number of NSRAEs				

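### The Overall correlation of marking with calculated dose ranks CD4+ and CD34+ doses together, so a difference between the two products can appear as a dose effect

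*SAP*

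**What the plan says.** SAP section 5 is a general presentation rule. Where of interest, data are pooled by target cell type (CD4 for 101, CD34 for 102 and 202) "in addition to presenting separately and overall". It mentions neither dose nor correlation.

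The operative text is section 7.2.1: "Correlation between OZ1 & LNL6 DNA-PCR (%) and calculated dose will be assessed using PROC CORR in SAS". The Spearman coefficient and its p-value are to be presented. The same section continues: "The above analyses will be performed for 102/202 combined and overall at each post infusion timepoint for the PP population". The Table 14.2.1.2 shell has matching columns, one for 102/202 and one for Overall, and none for 101 alone. Table 14.2.1.2a repeats the table for 202 only.

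On the products, section 6.4 says: "Patients in 101 originally received a single dose of transduced CD4+ lymphocytes and patients in 102 and 202 originally received a single dose of CD34+". It summarises time since infusion, dose, transduction efficiency and calculated dose by cell type (wording: "minimum, maximum and n by cell type (CD4 or CD34"). The Table 14.1.5 shell has a CD4 column and a CD34 column and no overall column.

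**The concern.** The SAP keeps the two cell types apart when it describes calculated dose and merges them when it correlates dose with marking. The pooled correlation is not stratified or adjusted, and no caution is attached to it. The only condition on running it is that enough patients have quantifiable data.

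A lymphocyte dose and a progenitor dose are doses of different products, even though the Table 14.1.5 shell labels both in cells per kg. Suppose one product was given at higher doses and also leaves higher marking. The 101 patients then sit at one end of both rankings, and the coefficient moves away from zero although marking is unrelated to dose within each product. If marking differs the other way, the sign reverses. Using ranks does not prevent this.

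At stake is the reading of one exploratory result: whether a reported dose–marking association reflects dose, or only which study the patient came from.

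**Working it through.** The plan states no sample size, power or expected correlation, so there is no figure to reproduce.

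**Inputs from the documents**
- Products: CD4+ in 101, CD34+ in 102 and 202 (SAP 6.4).
- Analysis: unstratified Spearman, 102/202 and Overall, at each timepoint (SAP 7.2.1, Table 14.2.1.2).
- Size of 101: not given; the shell headers show a single-digit placeholder.
- Size of the CD34 group: about half of 74 patients received OZ1 (Protocol 1.1), so about 37. Historical text in Protocol Appendix 3 mentions 8 patients from 102 in follow-up (used for scale only). That makes at most about 45.

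**Assumed:** the numbers with quantifiable marking, the dose and marking shifts between products, and a two-sided 0.05 level as a yardstick.

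**Step 1. Closed form.** Let n4 and n34 be the group sizes and N = n4 + n34. Suppose the products are fully separated on dose and on marking, with no association inside either.
- The mean ranks differ by N/2 on each axis.
- Between-group covariance of ranks = (n4·n34/N²)(N/2)² = n4·n34/4.
- Variance of ranks = (N² − 1)/12.
- Expected rho = 3·n4·n34/(N² − 1).

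| CD4 + CD34 | Calculation | Expected rho |
|---|---|---|
| 3 + 8 | 72/120 | 0.60 |
| 6 + 20 | 360/675 | 0.53 |
| 9 + 45 | 1215/2915 | 0.42 |
| 3 + 20 | 180/528 | 0.34 |
| 4 + 40 | 480/1935 | 0.25 |
| 3 + 45 | 405/2303 | 0.18 |
| 1 + 40 | 120/1680 | 0.07 |

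The artefact depends on the CD4 share and fades as that share falls.

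**Step 2. Simulation, doses fully separated, marking shifted.** No dose effect within product; 4,000 runs per setting.

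| CD34, CD4 | 0 SD | 1 SD | 2 SD |
|---|---|---|---|
| 20, 3 | about 5% | 12% | 22% |
| 30, 4 | about 5% | 14% | 30% |
| 40, 4 | about 5% | 13% | 25% |

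Mean rho at 2 SD is 0.21–0.29. A second set of runs gave 11–14% and 24–31%, which agrees within the one or two points of simulation error. With 1 CD4 patient and 20–40 CD34, the rate is 5–7% even at 2 SD. With 2 CD4 patients at 2 SD it is 9% beside 40 CD34, and a check with 20,000 runs gave 13% beside 20.

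**Step 3. Partial overlap in dose.** With both dose and marking shifted by 2 SD, the pooled test is significant in 11% (3 + 45), 34% (6 + 45), 49% (6 + 20) and 61% (9 + 45) of null runs. The CD34-only test on the same data stays at 4.5–6.2%. With a dose shift but no marking shift, the pooled test stays at about 5–6%. Both must differ for the artefact to arise.

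**Step 4. Which pooled alternative works.** Raw ranks taken within each study and then pooled are not safe. They run 1–4 in a study of 4 and 1–32 in a study of 32, so small-study patients get low ranks on both axes by construction. With no dose effect and no product difference, studies of 4, 8 and 32 give mean rho 0.39 and 79% significant. Studies of 8 and 32 give 0.27 and 37%. Ranks scaled by group size and centred within group give about 5–7%.

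**The case against.** The harm is limited, and much of the case for leaving the plan alone stands. The CD34-only column is printed beside Overall in Table 14.2.1.2, and Table 14.2.1.2a gives 202 alone; both are free of the CD4/CD34 mixture. Section 7.2.1 describes the relationships as explored. Protocol section 9 makes the analysis mainly descriptive and says only that factors may be assessed. A Data Review Meeting examines the marker data and documents decisions about these analyses. No decision in the plan depends on the Overall coefficient. Only patients with quantifiable marking enter, so 101 may contribute very few at a given visit. If it contributes none, Overall equals 102/202.

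These points lower the priority. They do not make the Overall coefficient interpretable, and a reader who sees it disagree with the CD34 column is not told which to believe.

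Two stronger readings are tempting and not supported:
- A reader might infer that the SAP would formally declare a dose–marking association at p<0.05. That sentence in section 7.2.1 belongs to the chi-square paragraph on gender and race. For Spearman, the coefficient and p-value are only presented.
- A reader might infer that the 102/202 column has the same defect. Both studies used CD34+ cells, section 5 groups them on that basis, and the documents give no dose or marking values showing that they differ.

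**Conclusion.** The Overall correlation of marking with calculated dose is confounded by cell type, and the SAP's own dose summaries avoid that mixture. The defect is confined to one column of one exploratory table.

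Whether it would mislead cannot be settled from the documents, and they do not show that the products actually differ in dose or marking. With 3–4 CD4 patients, 20–40 CD34 patients and fully separated doses, the null rate of p<0.05 is about 11–14% at a 1 SD marking difference and about 24–31% at 2 SD, against a nominal 5%. It would be higher with more CD4 patients and almost nominal with one. Severity is minor: worth changing because the change is nearly free.

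**What to change.** In SAP section 7.2.1 and Table 14.2.1.2, drop the Overall column for the calculated-dose correlation. Keep the 102/202 and 202-only results, and add 101 alone if enough of its patients have quantifiable marking.

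If a pooled figure is wanted, stratify by cell type: rank within CD4 and within CD34, scale the ranks by group size, centre them within each cell type, then correlate. Do not pool raw within-study ranks.

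The cost is a few lines of code, a changed table shell and one fewer pooled number. No within-product information is lost.

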## **6. DEMOGRAPHIC AND OTHER BASELINE CHARACTERISTICS**

### **6.1. DEMOGRAPHIC CHARACTERISTICS**

Date of birth, gender and race are recorded on the CRF as part of the initial study information.

Age (years) will be calculated using the formulae below and rounded to 1 decimal place.

$$\text{Age at Infusion} = (\text{Date of Infusion} - \text{Date of Birth}) / 365.25$$

$$\text{Age at Database Lock Cut Off} = (\text{Date of cut off}^* - \text{Date of Birth}) / 365.25$$

\* According to the current patient visit schedule this is due 13FEB2016 (window period +/- 6 weeks). If a patient has discontinued or died before the date of cut off, the date of Study Discontinuation will replace date of cut off.

Age will be summarized using descriptive statistics, mean, median, standard deviation (SD), minimum, maximum and n separately for patients in 101, 102, 202 and overall.

The number and percentage of patients within each category for gender and race will be summarized for patients in 101, 102, 202 and overall.

Demography will be summarized for PP population.

### **6.2. PATIENT DISPOSITION AND WITHDRAWALS**

The number and percentage of patients who are ongoing and have never discontinued, discontinued and re-instated, and discontinued and never re-instated will be presented separately for 101, 102, 202 and overall. The primary reason for withdrawal will also be presented for those patients who have discontinued.

A table detailing the visit and date of last visit prior to discontinuation together with the reason for discontinuation of each individual patient who discontinued during the long term follow-up will also be presented.

Patients may be discontinued from the long term follow-up for any of the following reasons:

- Patient request
- Were randomized to the placebo treatment arm (202 only)

<Protocol: Janssen OZ1-HV1-101/102/202>

<INC code: 1003733>

<SAP Version: 3.0>

---

- Lost to follow-up
- Regulatory authority request
- Study termination
- Other

Patient disposition and withdrawal data will be summarized for all patients.

The number and percentage of patients assigned to each analysis population will be summarized separately for 101, 102 and 202 and overall.

### 6.3. SIGNIFICANT MEDICAL HISTORY

Information relating specifically to HIV-1 infection will be recorded in the significant medical history (body system Immunological/Rheumatological) as part of the initial study information.

Time since HIV-1 infection will be summarized by descriptive statistics, mean, median, standard deviation (SD), minimum, maximum and n separately for 101, 102 and 202 and overall for the Safety and PP populations. Time since HIV-1 infection will be derived as follows:

$$\text{Time since HIV-1 infection (yrs)} = \text{Year of diagnosis} - (\text{Date of Database lock} + 1)$$

Data recorded for other body systems will be listed only.

### 6.4. OTHER INITIAL STUDY INFORMATION

Treatment details (date of infusion, dose, treatment and transduced efficiency) from the original studies are recorded as part of the initial study information. Patients in 101 originally received a single dose of transduced CD4+ lymphocytes and patients in 102 and 202 originally received a single dose of CD34+ cells.

Time since infusion (years) will be derived using the following formula:

$$(\text{Date of Last Visit in Long Term Follow-up} - \text{Date of Infusion}) / 365.25$$

Time since infusion, dose, transduction efficiency and calculated dose will be summarized using descriptive statistics, mean, median, standard deviation, minimum, maximum and n by cell type (CD4 or CD34). Calculated dose will be derived as follows:

$$\text{Dose (CD4+ or CD34+)} / 100 \times \text{transduction efficiency}$$

<Protocol: Janssen OZ1-HV1-101/102/202>

<INC code: 1003733>

<SAP Version: 3.0>

---

## 7. EFFICACY

### 7.1. MARKING IN PERIPHERAL BLOOD MONONUCLEAR CELLS

PBMC analysis (OZ1 & LNL6 DNA PCR (marking)) will be performed at 2 years post infusion or the nearest timepoint before starting the long term follow-up and at each 6 monthly visit up to 5 years post infusion and annually there after. Analyzed samples for gene detection will be classified as either not done, not detected or detected. If detected genes are found these will further be classified as to whether they are below the limit of quantification or not. Samples below the limit of quantification will be classified as either 1/3 (genes detected in 1 of the 3 triplicates of the sample), 2/3 (genes detected in 2 of the 3 triplicates of the sample) or 3/3 (genes detected in 3 of the 3 triplicates of the sample). For samples above the limit of quantification the percentage detected will be recorded for OZ1 & LNL6 DNA-PCR.

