This will be a follow-up study of patients previously enrolled in the OTH/OZ1-INT-1 trial. All patients in this protocol will be reviewed at six monthly intervals until year 5 post infusion. Thereafter all patients will be reviewed annually, on the anniversary of the infusion until withdrawal or study completion. Patients who were enrolled in the placebo arm will be discontinued after OTH/OZ1-INT-1 has been unblinded.

STUDY POPULATION

Participants in the OTH/OZ1-INT-1 Phase II study entitled “A Randomized Phase II, double blind, controlled trial to evaluate the safety and efficacy of autologous CD34+ hematopoietic progenitor cells transduced with placebo or an anti-HIV-1 ribozyme (OZ1) in patients with HIV-1 infection” will be asked to consent to continue safety monitoring and gene marking as described in this protocol.

DOSAGE AND ADMINISTRATION

All participants of the OTH/OZ1-INT-1 Phase II study received a single dose of placebo or OZ1 transduced CD34+ cells.

SAFETY EVALUATIONS†

Follow-up will be conducted as per current FDA/Center for Biologics Evaluation and Research (CBER) recommendations. Evaluations will include monitoring for related adverse events such as the development of replication competent retrovirus (RCR), predominant integration sites and insertional oncogenesis. Blood samples will be collected for archival storage for assessment of replication competent retrovirus (RCR) and other safety testing as necessary.

EFFICACY EVALUATIONS

Ongoing analysis of quantitative marking of the gene transfer product (OZ1 and LNL6) in peripheral blood mononuclear cells (PBMC) will be performed as part of the testing of predominant integration sites. These marking data will also be analyzed independently of the integration analysis to detect changes in the number of cells carrying the gene transfer product.

TIME AND EVENTS SCHEDULE

Follow up visits may be part of routine clinic visits where possible, but must be performed as described in the Time and Events Schedule. Additional unscheduled visits will be made if clinical or biological findings, as described in this protocol, require additional evaluation or investigation or as directed by the Investigator.

OZ1: Clinical Protocol OZ1-HV1-202 Amendment 4; 07 June 2017

TIME AND EVENTS SCHEDULE[†]

Follow up visit	Yr 2.5	Yr 3	Yr 3.5	Yr 4	Yr 4.5	Annual Yr 5+ /End-of- Study ⁴
Clinical history and examination	X	X	X	X	X	X
Complete Blood Count/Differential and Platelets	X	X	X	X	X	X
Plasma archive		X		X		X

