1. INTRODUCTION

1.1 Background[†]

OZ1 is a Moloney Murine Leukemia Virus based retroviral vector (LNL6) containing a gene that encodes an anti-HIV-1 ribozyme directed against the human immunodeficiency virus type 1 (HIV-1) regulatory gene *tat*.^{13,14,15} A Phase I study demonstrated that the introduction of OZ1 into CD34+ cells *ex vivo* is technically feasible and safe.¹ The international, multi-center, Phase II, randomized, double-blind trial, OTH/OZ1-INT-1, was initiated to investigate the safety and efficacy of OZ1-transduced autologous CD34+ cells in patients with HIV-1 infection.⁹ One patient was enrolled in a Phase II protocol comparing the retroviral vector alone (LNL6) and OZ1. In a protocol amendment, OTH/OZ1-INT-1 became a placebo-controlled trial. Of the 74 patients to be enrolled in the placebo controlled protocol, approximately half received a placebo and half OZ1. The primary efficacy end point is the difference in viral load between the two groups at weeks 47 and 48 post-infusion. Patients continue in the OTH/OZ1-INT-1 treatment interruption follow-on phase until week 100 post-infusion as long as the viral load remains below 100,000 copies/ml, the CD4+ cell count is greater than 150 cells/mm³ and there are no other reasons to recommence antiretroviral therapy. At the end of the OTH/OZ1-INT-1 study (week 100 post-infusion), patients are invited to enter this long term follow-up (LTFU) protocol.

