2. OBJECTIVES

1. To undertake long term safety monitoring for any development of:
 - a. Clonal expansion of cells with a predominant OZ1 insertion site
 - b. Insertional oncogenesis
2. To archive/store plasma and PBMC samples for other safety testing that may be required.
3. To assess quantitative marking of the gene transfer product in PBMCs over time.

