6. CONCOMITANT THERAPY AND ACTIVITIES

Information on current medications or other therapies will not be collected, unless required for submission of a Serious Adverse Event report.

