9.1 Efficacy Evaluation[†]

Ongoing analysis of quantitative marking of the gene transfer product (OZ1 and LNL6) in peripheral blood mononuclear cells will be performed as part of the testing of OZ1 or LNL6 vector integration sites. These data will be used to independently assess changes in the number of peripheral blood mononuclear cells that carry the gene transfer product over time.

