### **8.4. CBC/DIFFERENTIAL AND PLATELETS**

CBC/differential and platelets (haematocrit, red blood count, haemoglobin, white blood count, platelets, neutrophils, lymphocytes, monocytes, eosinophils, basophils) will be recorded as part of the initial study information and at each follow-up visit. CBC/differential and platelets data will be recorded in the units as pre-printed on the CRF. No conversion of these data to Standard International Units will be required.

CBC/differential and platelets values and change from baseline (2 years post infusion or nearest timepoint before starting long term follow-up) values will be summarized overall.

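### The protocol asks how the number of PBMC carrying the product changes over time; the SAP derives no such number and plans no within-patient change in marking on any scale

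*SAP*

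**What the plan says.** **Protocol.** Section 9.1 says the marking data will be used to "independently assess changes in the number of peripheral blood mononuclear cells that carry the gene transfer product over time". The synopsis (Efficacy Evaluations) and the visit procedures in 7.1 put it this way: "These marking data will also be analyzed independently of the integration analysis to detect changes in the number of cells carrying the gene transfer product". Footnote 2 of the Time and Events Schedule has a shorter version, and the SAP repeats that footnote under both of its visit schedules (Tables 1 and 2). Objective 3 is less specific: "To assess quantitative marking of the gene transfer product in PBMCs over time". It names neither a number nor a percentage. Protocol 9 makes descriptive summary of change over time the main focus of the analysis.

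**SAP.** Section 7.1 classifies each analysed sample as not detected, detected below the limit of quantification (one, two or three of the triplicates), or quantifiable. For the last group: "For samples above the limit of quantification the percentage detected will be recorded for OZ1 & LNL6 DNA-PCR". Section 7.2.1 then plans:

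- patients per detection category at each visit (Table 14.2.1.1, and 14.2.1.1a for study 202);
- a listing of the quantifiable values (Listing 16.2.5.2.2), with the "relationship between the % marking and calculated dose, age at infusion, gender and race explored";
- Spearman correlations of the percentage with calculated dose, age and time since infusion, and chi-square or Fisher tests of quantifiable detection by gender and race, at each visit;
- plots over time of the percentage of patients with any detected result.

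SAP 8.4 says that the CBC and differential, including lymphocytes and monocytes, "will be recorded as part of the initial study information and at each follow-up visit". Change from the 2-year baseline is planned for those counts. SAP 10.2 declares no change to the planned analyses.

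**The concern.** Marking is the only item under the protocol's efficacy evaluations. The quantity that the protocol says it will follow, how many cells carry the product, appears in none of the SAP's outputs.

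A percentage can stand in for a number only while the PBMC count is stable, and in study 202 there is some reason to doubt that. Protocol 1.1 says: "Patients continue in the OTH/OZ1-INT-1 treatment interruption follow-on phase until week 100 post-infusion", subject to viral load, CD4 count and no other reason to restart therapy. Two years is about 104 weeks (2 × 52), so for patients still off therapy at week 100 the 2-year baseline comes close to the end of the interruption. If therapy is resumed later, counts may move. Protocol 6 says: "Information on current medications or other therapies will not be collected", except where a serious adverse event report needs it, so such a shift could not generally be explained from the treatment record.

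The final report could therefore describe which patients have detectable marking without saying whether the number of marked cells in a patient rose, fell or held. A reader wanting that answer would have only the listed percentages.

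**Working it through.** **1. No figure to reproduce.** The documents state no marking level, cell count, sample size or power. The check sets the outputs against the stated purpose and then works through the arithmetic linking the two scales.

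**2. What each planned marking output contains.**

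| Output | Unit summarised | Number of marked cells? | Within-patient change? |
|---|---|---|---|
| Table 14.2.1.1 / 14.2.1.1a | Patients per detection category, by visit | No | No |
| Listing 16.2.5.2.2 | % of cells, quantifiable samples | No | Not computed |
| Table 14.2.1.2 / 14.2.1.2a, Spearman | % of cells, across patients at one visit | No | No |
| Table 14.2.1.2 / 14.2.1.2a, chi-square or Fisher | Patients with or without quantifiable marking | No | No |
| Figures 14.1.1 to 14.1.3 | % of patients with a detected result | No | No |

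The correlation with time since infusion does not fill the gap. SAP 6.4 defines that time as (date of last follow-up visit − date of infusion) / 365.25, which is one fixed value per patient. The correlation is run across patients within a visit, so it says nothing about how a patient's marking moves between visits.

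**3. The two scales.** Let p be the percentage marked and C the PBMC count per µL, approximated by lymphocytes + monocytes.

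- Number: N = (p / 100) × C
- Change: N₁/N₀ = (p₁/p₀) × (C₁/C₀)

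If the percentage changes by a ratio r, the number moves the other way when C₁/C₀ > 1/r (for r < 1) or C₁/C₀ < 1/r (for r > 1):

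- 10% fall: 1/0.90 = 1.11, so the number rises if the count rises more than 1.11-fold
- 20% fall: 1/0.80 = 1.25-fold
- 50% fall: 1/0.50 = 2.0-fold
- 25% rise: 1/1.25 = 0.80, so the number falls if the count drops below 0.80-fold

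**4. Illustration.** Every count and marking level here is an assumption. Percentage 0.10 → 0.08 (−20%), starting count 1,500/µL, so N₀ = 0.0010 × 1,500 = 1.50/µL.

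| Later count per µL | N₁ = 0.0008 × count | Change in number |
|---|---|---|
| 1,500 | 1.20 | −20% |
| 1,800 | 1.44 | −4% |
| 1,875 | 1.50 | 0% |
| 2,250 | 1.80 | +20% |
| 3,000 | 2.40 | +60% |

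Two limiting cases, with the count doubling from 1,500 to 3,000/µL:

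- If marked cells stay at 1.5/µL, the percentage falls from 0.10 to 0.05 although the number has not changed.
- If marked and unmarked cells grow in proportion, the percentage stays at 0.10 while the number goes from 1.5 to 3.0/µL.

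A small drift in count changes the size of the answer but not its direction. Reversal needs a count change beyond 1/r.

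**The case against.** The strongest reply is that this is a mismatch of wording. Objective 3 speaks of quantitative marking, and the protocol ties quantitative marking to a PCR result expressed as a percentage of the test cells. The protocol never mentions cells per µL or combining PCR with the CBC, so its references to number may be loose wording for marking level. Protocol 9 also leaves the technique open. Finally, the SAP lists both CBC (16.2.11) and quantifiable marking (16.2.5.2.2) by patient, so a reader could do the multiplication.

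Part of this stands. Objective 3 does not fix the scale, and correcting the wording is a legitimate remedy. But footnote 2 of the Time and Events Schedule uses percentage for the 1% threshold and number for the marking analysis, which makes loose wording harder to assume. The listings leave a stated analysis to the reader. The CBC summary (Table 14.5.X) is shown only overall across the three studies, so it cannot be matched to a patient's marking. Reading number as percentage would not close the gap either, because change in percentage is not summarised.

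The practical objections also stand: lymphocytes + monocytes only approximates PBMC, and SAP 7.2.1 itself allows that there may be too few quantifiable patients for a meaningful analysis.

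Stronger readings are tempting, and the documents do not support them:

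- **That the SAP analyses only the percentage marked and will report the wrong direction of change.** Its by-visit table and plots count patients, and no change in percentage is planned, so no planned estimate can point the wrong way. The risk lies in what a reader infers from the listing.
- **That objective 3 cannot be met.** Its wording does not require a number.
- **That resumed therapy will dilute the percentage.** The interruption argument concerns only study 202 patients still off therapy at week 100, whose number is not given. Dilution also needs marked and unmarked cells to change at different rates, and the documents give no evidence on that.

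**Conclusion.** The concern holds as a gap between stated purpose and planned output. Protocol and SAP both say that change in the number of marked cells will be assessed; SAP 7.1 and 7.2.1 produce neither that number nor a within-patient change on either scale, and no departure is declared.

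The size in this trial cannot be determined from the documents. The thresholds in the working follow from the identity alone; the illustrative percentages and counts are assumptions. Whether counts moved enough to matter depends on each patient's CBC.

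This should be settled before the final analysis. Monitoring for predominant integration sites, RCR and adverse events does not depend on it.

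**What to change.** 1. **State the scale** in SAP 7.2.1. If number is meant, derive for each quantifiable sample: marked cells/µL = % marked / 100 × (lymphocytes + monocytes from the same-visit CBC), described as an approximation of PBMC. SAP 8.4 keeps CBC data in the units printed on the CRF, so state the conversion if the differential is recorded as a percentage of white cells.
2. **Present it.** Add the variable to Listing 16.2.5.2.2. Add rows to Tables 14.2.1.1 and 14.2.1.1a, or a companion table (they now hold only patient counts), giving the percentage and the number by visit with change from the 2-year baseline.
3. **Do not hide loss of marking.** At each visit show how many patients are not detected or below quantification, including how many of those were quantifiable at baseline. Change among pairs quantifiable at both visits would otherwise leave out the patients whose marking fell.
4. **Tie the conclusion to the variable.** Base any statement about change in the number of marked cells on it. If the sponsor means percentage, correct the wording in the protocol and SAP, record this in SAP 10.2, and still summarise change in percentage.

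**Cost.** One derived variable and a few table rows, from data already collected at baseline and at the same visits; no new samples. The variable is missing where the CBC is missing or the sample is below quantification, and it may be available for few patients.
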